2. STUDY DESIGN

Study GX29176 is a Phase III, double-masked, multicenter, randomized, sham-injection-controlled study evaluating the efficacy and safety of a 10 mg dose of lampalizumab administered every 4-weeks (Q4W) or every 6-weeks (Q6W) by intravitreal injection during a 96-week (approximately 2 year) treatment period in patients with GA secondary to AMD. The study consists of a screening period (of up to 28 days duration), followed by a 96-week treatment period.

Approximately 936 patients will be randomized into the study at approximately 140 investigational sites located globally. The study will enroll both CFI-profile biomarker-positive and CFI-profile biomarker-negative patients (see Section 2.2); enrollment will be in a ratio of 1.5:1 for biomarker-positive patients relative to biomarker-negative patients. Eligible patients are randomized in a 2:1:2:1 ratio to receive 10 mg lampalizumab Q4W, sham Q4W, 10 mg lampalizumab Q6W, or sham Q6W during the 96-week treatment period. Study treatment is given Day 1 to Week 92 for the Q4W treatment arms and Day 1 to Week 90 for the Q6W treatment arms, with a final study visit at Week 96 for all patients.

Efficacy, safety, and pharmacokinetic (PK) measures are assessed throughout the treatment period, as detailed in the Schedule of Assessments (see study protocol).

Further study design details are provided in the study protocol.

2.1 ENDPOINTS/OUTCOME MEASURES

Unless otherwise specified, ocular efficacy outcome measures refer to the study eye.

2.1.1 Primary Efficacy Endpoint

The primary efficacy endpoint is change from baseline in GA area at 1 year (48-weeks) as assessed by fundus autofluorescence (FAF).

2.1.2 Secondary Efficacy Endpoints

The following secondary efficacy endpoints will be assessed over time up to Week 96, with formal statistical testing at Week 96. Hypothesis testing for three key secondary endpoints will be performed in the order specified in Section 4.5.2.1 based on the Week 96 timepoint.

- Change from baseline in number of absolute scotomatous points as assessed by mesopic microperimetry
 - Assessed for subset of patients at selected study sites only. Endpoint will be evaluated based on pooled data from GX29176 and GX29185.

- Change from baseline in mean macular sensitivity as assessed by mesopic microperimetry
 - Assessed for subset of patients at selected study sites only. Endpoint will be evaluated based on pooled data from GX29176 and GX29185.
- Change from baseline in best corrected visual acuity (BCVA) as assessed by the Early Treatment Diabetic Retinopathy Study (ETDRS) chart at a starting distance of 4 m
- Patients with < 15 letters loss from baseline in BCVA score as assessed by the ETDRS chart at a starting distance of 4 m
- Change from baseline in low luminance visual acuity (LLVA) as assessed by the ETDRS chart at a starting distance of 4 m
 - Note: In the protocol, LLVA was referred to as BCVA score as assessed by ETDRS chart under low luminance conditions.
- Patients with < 15 letters loss from baseline in LLVA score as assessed by the ETDRS chart at a starting distance of 4 m
- Change from baseline in binocular maximum reading speed as assessed by Minnesota low-vision reading test (MNRead) or Radner Charts
- Change from baseline in monocular maximum reading speed as assessed by MNRead or Radner Charts
- Change from baseline in National Eye Institute Visual Functioning Questionnaire 25-item Version (NEI VFQ-25) composite score
- Change from baseline in NEI VFQ-25 near activity subscale score
- Change from baseline in NEI VFQ-25 distance activity subscale score
- Change from baseline in Mean Functional Reading Independence (FRI) Index score

2.1.3 Exploratory Efficacy Endpoints

The following exploratory efficacy endpoints will be assessed over time up to Week 96, with formal statistical testing at Week 96.

- Patients with < 20% increase from baseline in GA area as assessed by FAF
- Change from baseline in GA area over time (all additional timepoints [Weeks 24, 36, 72, and 96]) as assessed by FAF
- Change from baseline in number of absolute or relative scotomatous points as assessed by mesopic microperimetry
 - Assessed for subset of patients at selected study sites only. Endpoint will be evaluated based on pooled data from GX29176 and GX29185.
- Percent change from baseline in binocular maximum reading speed as assessed by MNRead or Radner Charts

- Patients with at least a 2-level decline from baseline in binocular maximum reading speed (based on the following levels: <40, ≥ 40 to <60, ≥ 60 to <80, ≥ 80 to <120, ≥ 120 to <160, ≥ 160 wpm) as assessed by MNRead or Radner Charts
- Percent change from baseline in monocular maximum reading speed as assessed by MNRead or Radner Charts
- Patients with at least a 2-level decline from baseline in monocular maximum reading speed (based on the following levels: <40, ≥ 40 to <60, ≥ 60 to <80, ≥ 80 to <120, ≥ 120 to <160, ≥ 160 wpm) as assessed by MNRead or Radner Charts
- Change from baseline in binocular critical print size as assessed by MNRead or Radner Charts
- Change from baseline in monocular critical print size as assessed by MNRead or Radner Charts
- Change from baseline in binocular reading acuity as assessed by MNRead or Radner Reading Charts
- Change from baseline in monocular reading acuity as assessed by MNRead or Radner Reading Charts
- Patients with no decline from baseline in FRI Level score
- Patients with visual function worsening, as defined by (i) a ≥5 letter decrease in BCVA (as assessed by the ETDRS chart), AND (ii) a ≥20% decrease in monocular maximum reading speed (as assessed by MNRead or Radner Reading Charts)
- Patients with overall disease worsening, as defined by (i) a ≥5 letter decrease in BCVA (as assessed by the ETDRS chart), AND (ii) a ≥20% decrease in monocular maximum reading speed (as assessed by MNRead or Radner Reading Charts), AND (iii) a ≥20% increase in GA area (as assessed by FAF)

2.1.4 Supplemental Efficacy Endpoints Related to Primary Endpoint

The following efficacy endpoints, closely related to the primary efficacy endpoint, will be assessed over time up to Week 48 to provide supplemental information to the primary endpoint analysis. The endpoints will also be assessed over time up to Week 96 at the time of the final study analysis.

- Rate of change in GA area (growth slope) as assessed by FAF
- Change from baseline in square root of GA area as assessed by FAF
- Percent change from baseline in GA area as assessed by FAF

2.1.5 Pharmacokinetic and Pharmacodynamic Outcome Measures

As specified in the protocol, the PK outcome measure for this study is serum lampalizumab concentrations over time. Total lampalizumab and complement factor D (CFD) levels in aqueous humor are specified as an exploratory outcome measure. (Note, aqueous humor samples are only available for the subset of patients who consented to optional aqueous humor sampling.)

2.1.6 Safety Endpoints

The safety outcome measures are as follows:

- The incidence and severity of ocular adverse events
- The incidence and severity of non-ocular adverse events
- Changes and abnormalities in electrocardiogram (ECG) parameters
 - Assessed through Week 24 for patients at selected sites who have undergone ECG evaluation (approximately 100 patients in total)
- The incidence of anti-drug antibodies

2.1.7 Diagnostic Outcome Measures

The evaluation of the predictive value of the CFI-profile biomarker will be assessed through the evaluation of the primary efficacy endpoint. The evaluation of the prognostic value of the CFI-profile biomarker will be based on the primary clinical outcome of change from baseline in the GA area as measured by FAF in the sham arm.

In addition, the following exploratory diagnostic outcome measures are specified:

- The association of genetic variants in CFI and complement-pathway genes with disease characteristics and response to lampalizumab
- The relationship of genetic variants in CFI and complement-pathway genes to levels in the blood of mRNA and proteins of CFI and complement-pathway genes

2.2 BIOMARKER CONSIDERATIONS

Exploratory genetic analyses of data from the Phase II Study CFD4870g suggested that a biomarker-defined population (CFI-profile biomarker-positive) may have more rapid disease progression and potentially derive greater efficacy benefit from lampalizumab than the population that is negative for the biomarker (CFI-profile biomarker-negative). In order to further evaluate this hypothesis, this Phase III study (GX29176) will enroll both CFI-profile biomarker-positive and biomarker-negative patients; enrollment will be in a ratio of 1.5:1 for CFI-profile biomarker-positive patients relative to CFI-profile biomarker-negative patients.

Complement factor I profile is based on the common genetic variants of CFI, complement factor H (CFH), and complement component 2/complement factor B (C2/CFB). The following two patient groups are defined (see [Table 1](#)):

- **CFI profile biomarker-positive patients:** Patients who are carriers of CFI risk allele, who are also risk allele carriers at CFH and/or C2/CFB.
- **CFI profile biomarker-negative patients:** Patients who are (i) non-carriers of the CFI risk allele or (ii) carriers of the CFI risk allele, who are non-carriers of the risk alleles at both CFH and C2/CFB.

Table 1 Definition of Biomarker Status Using the CFI Profile Test

	CFI	CFH	C2/CFB
CFI profile biomarker-positive	+	+	+
	+	+	-
	+	-	+
CFI profile biomarker-negative	+	-	-
	-	+	+
	-	+	-
	-	-	+
	-	-	-

C2 = complement component 2; CFB = complement factor B; CFH = complement factor H; CFI = complement factor I.

Note: “+” indicates that the patient is a risk-allele carrier (i.e., heterozygous or homozygous for the risk allele) and “-” indicates that the patient is a non-carrier of the risk allele.

For this study, CFI-profile biomarker status is determined using the investigational cobas[®] CFI Profile Clinical Trial Assay (CTA). The cobas[®] CFI Profile CTA biomarker status results are used for patient enrollment (to achieve a 1.5:1 ratio for biomarker-positive relative to biomarker-negative patients) and for stratification of patients at randomization. In addition, all biomarker-related analyses specified in this SAP will be performed on the basis of CFI profile results from the cobas[®] CFI Profile CTA.

Enrollment of both biomarker-positive and biomarker-negative patients allows for evaluation of the treatment benefit in both patient groups, as well as the overall enrolled population. The hypotheses of interest and order of hypothesis tests for the primary efficacy endpoint are specified in Section 4.5.1, and take precedence over that specified in the study protocol. In addition to data from exploratory analyses of Study CFD4870g, interim data from the epidemiological Study GX29633 were considered for the order of hypothesis testing.

2.3 SAMPLE SIZE

2.3.1 Determination of Sample Size

Approximately 936 patients will be enrolled in the study. Patients are randomized in a 2:1:2:1 ratio to receive treatment with lampalizumab Q4W, sham Q4W, lampalizumab Q6W, or sham Q6W. Data from the two sham treatment arms will be pooled in the analysis.

The study was originally sized to achieve adequate power for detecting a meaningful reduction rate in the GA area growth for a given lampalizumab dosing frequency compared with pooled sham within each of the biomarker-positive and biomarker-negative groups and to meet health authority requirements for the size of the safety database. At the time of the study design, sample size and power calculations used assumptions based on results from the Phase II Study CFD4870g. For details of the determination of sample size, see study protocol Section 6.1.

As outlined in Section 6.1, the protocol also specified that the Sponsor may conduct a masked evaluation of the variance of the primary efficacy endpoint and study dropout rate before the end of enrollment, with the intent to potentially increase the study sample size if deemed necessary in order to maintain the desired study power. However, such an evaluation was not conducted and the sample size of the study remained unchanged from that originally planned.

2.3.2 Estimated Power Based on Information from Study GX29633

The primary efficacy endpoint is the change from baseline in GA area at 1 year (48 weeks) as assessed by FAF. As specified in Section 4.5.1, the primary efficacy objectives will be assessed by analysis of the primary efficacy endpoint in the overall patient population and in the biomarker-positive group for each dosing frequency separately.

[Table 2](#) summarizes the power and minimum detectable difference for the primary endpoint analysis when evaluated for the overall patient population and the biomarker-positive group using progression rates and variability assumptions based on data from Study GX29633, a prospective epidemiological study of the progression of GA secondary to AMD (May 2017 interim analysis). Namely, calculations assumed a progression rate (mean change from baseline in GA area at 48-weeks) of 2.08 mm² for both the biomarker-positive and biomarker-negative patient groups and a SD of 1.53 mm² for the change from baseline in GA area at 48-weeks. With these assumptions, 312 patients per lampalizumab treatment arm and 156 patients per sham arm will provide 88% power to declare a difference between each lampalizumab treatment arm and the pooled sham arm in the overall patient population for a targeted difference of 0.42 mm² (approximately 20% reduction relative to sham control) in the change from baseline in GA area at 48 weeks ([Table 2](#)). Estimated power to detect specified differences in the primary efficacy endpoint within the biomarker-positive

patient population is as shown in Table 2. Calculations were based on two-sided t-tests at the $\alpha=0.0496$ level (after adjustment for the four data reviews conducted by the iDMC prior to analysis of the primary efficacy endpoint), with the assumption of a 15% dropout rate by 48 weeks.

Table 2 Power and Minimum Detectable Difference for Analysis of Primary Endpoint Using Assumptions Based on the Epidemiological Study GX29633

Endpoint Summary and Population	Target Treatment Effect	Two-Sided $\alpha=0.0496$	
		Power	MDD
Mean change from baseline in GA area at 1 year (48 weeks) in all patients (n=312 per arm)	$\Delta=0.42 \text{ mm}^2$ (approximately 20% ^a reduction) SD= 1.53	88%	0.26 mm^2 (approximately 13% ^a reduction)
Mean change from baseline in GA area at 1 year (48 weeks) in biomarker-positive patients (n= 188 per arm)	$\Delta=0.83 \text{ mm}^2$ (approximately 40% ^a reduction) SD= 1.53	> 95%	0.34 mm^2 (approximately 16% ^a reduction)

GA=geographic atrophy; MDD=minimum detectable difference.

The sample size takes into account the dropout rate of 15% by 48 weeks. The power and MDD are for each comparison between one lapanzumab treatment arm and the pooled sham arm.

^a Relative to the sham arm and assuming the mean change from baseline in GA area at 48 weeks is 2.08 mm^2 for both the biomarker-positive and biomarker-negative patient groups.

2.4 ANALYSIS TIMING AND UNMASKING

The analysis of data from the first 48-weeks of the study will be performed when (i) all patients have completed study visits through Week 48 or have discontinued from the study prior to Week 48 and (ii) all data from the first 48-weeks of the study are in the database and have been reviewed per the Data Quality Review Plan and verified per the Trial Monitoring Plan.

At that time, Sponsor personnel who are analyzing data from the first 48-weeks of the study will be unmasked to treatment assignment. To maintain data integrity for the remainder of the study, internal guidelines are to be followed to avoid unnecessary unmasking of investigator site staff or patients.

Analyses will include formal hypothesis testing of the primary efficacy endpoint (anatomic outcome) at Week 48. Secondary and exploratory endpoints (visual function outcomes) will be evaluated based on 48-week data in an exploratory manner, although formal statistical testing for these endpoints will be at Week 96. An analysis of the 48-week safety data will also be performed.

The second year of the study will be ongoing at the time of the 48-week primary analysis. An analysis of the second year safety data that is available at the time of the 48-week primary analysis will be performed; it will include all safety data after Week 48 and up to a single specified calendar cutoff date. Such results will be reported with, but separate from, the 48-week study results to provide additional safety information for lampalizumab.

The final study analysis based on data from the complete study will be performed when all patients have either completed the 2-year study period (i.e., study visits through Week 96) or have discontinued early from the study, all data from the study are in the database, and the database is locked. Secondary and exploratory endpoints (visual function outcomes) will be analyzed based on Week 96 data. At the time of the final analysis, safety summaries will be produced based on cumulative Week 96 data.

Aggregate results of the 48-week analysis may be reported to the public before completion of the study. However, patients, masked study site personnel, and central reading center personnel will remain masked to individual treatment assignment until after the study is completed (after all patients have either completed Week 96 or discontinued early from the study), the database is locked, and the study analyses are final. Sponsor study team members who are aware of individual patient-level treatment assignments and have direct contact with the study site will sign a non-disclosure form and will not reveal treatment assignment information to site staff.

[Table 3](#) provides an overview of the timing for the planned analyses.

Table 3 Timing of Planned Analyses

Analysis	Timing of Analysis	Adjusted Two-Sided Alpha Level
Primary	All patients complete 1 year (48 week) assessment or discontinue study early	0.0496 for primary endpoint tested at Week 48
Final	All patients complete 2 year (96 week) assessment or discontinue study early	0.0496 for secondary and exploratory endpoints tested at Week 96

Note: Secondary and exploratory efficacy endpoints (visual function outcomes) will be evaluated based on Week 48 data in an exploratory manner, although formal statistical testing for these endpoints will be at Week 96.

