4.5.1.1	Overall Patient Population Analysis.....	18
4.5.1.2	Biomarker Subgroup Analyses	19
4.5.1.3	Other Subgroup Analyses.....	19
4.5.1.4	Sensitivity Analyses	20
4.5.1.5	Supplemental Analyses	23
4.5.2	Secondary Efficacy Endpoints.....	23
4.5.2.1	Type I Error Management.....	25
4.5.2.2	Subgroup Analyses	26
4.5.3	Exploratory Efficacy Endpoints	27
4.5.4	Additional Biomarker Analyses	28
4.6	Pharmacokinetic and Pharmacodynamic Analyses.....	29
4.7	Safety Analyses.....	29
4.7.1	Exposure of Study Medication.....	29
4.7.2	Adverse Events	30
4.7.3	Laboratory Data.....	31
4.7.4	Immunogenicity	31
4.7.5	Ocular Assessments.....	31
4.7.6	ECG Results.....	31
4.8	Interim Analyses	32
5.	REFERENCES	32

LIST OF TABLES

Table 1	Definition of Biomarker Status Using the CFI Profile Test.....	9
Table 2	Power and Minimum Detectable Difference for Analysis of Primary Endpoint Using Assumptions Based on the Epidemiological Study GX29633.....	11
Table 3	Timing of Planned Analyses.....	12

1. **BACKGROUND**

The purpose of this document is to provide details of the planned analyses for Study GX29176 (Chroma). Analyses for both the primary study analysis and the final study analysis are described.

The primary study analysis will be based on complete data from the first 48-weeks of the study, and performed after all patients have completed 48-weeks in the study or discontinued early, and all corresponding data have been entered into the database, reviewed, and verified. Analysis will include hypothesis testing of the primary efficacy endpoint (anatomic outcome) at Week 48. Secondary and exploratory endpoints (visual function outcomes) will be evaluated based on 48-week data in an exploratory manner, although formal statistical testing for these endpoints will be at Week 96. An analysis of the 48-week safety data will be performed.

At the time of the primary 48-week analysis, the second year of the study will be ongoing. An analysis of the available second year safety data (after Week 48 and up to a specified clinical cutoff date) will also be performed. Such results will be reported with, but separate from, the 48-week study results to provide additional safety information for lampalizumab.

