3.2.2 Independent Data Monitoring Committee

An independent Data Monitoring Committee (iDMC) monitors safety and study conduct on an ongoing basis. Members of the iDMC are external to the Sponsor and follow a charter that outlines the iDMC roles and responsibilities. The iDMC meets approximately every 6 months (frequency adjustable as required) to review unmasked safety and study conduct data prepared by an external iDCC. Further, the iDMC may review efficacy data if deemed necessary to assess the benefit-risk profile of lampalizumab.

The iDMC may recommend stopping the study early for safety reasons. No formal efficacy or futility analysis is planned for the study. While there are no formal efficacy or futility analyses, per FDA request, a nominal Type I error penalty of 0.0001 will be taken for each time the iDMC reviews unmasked data reports prior to the formal analysis of the primary efficacy endpoint. At the time of the primary efficacy endpoint analysis, four scheduled data reviews will have been conducted by the iDMC (July 2015, February 2016, August 2016, and March 2017); therefore, analyses of the primary efficacy endpoint will be performed at $\alpha = 0.0496$.

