4.5.2.1 Type I Error Management

Significance testing for secondary efficacy endpoints will be gated on the success of the primary efficacy endpoint evaluated at Week 48. Secondary efficacy endpoints will be tested at Week 96 for the lampalizumab dose frequency or frequencies (Q4W or Q6W) and patient populations (overall or biomarker-positive) found to demonstrate statistically significant treatment effect for the primary efficacy endpoint.

The following secondary efficacy endpoints will be tested in the order listed below:

- Change from baseline in number of absolute scotomatous points at Week 96 as assessed by mesopic microperimetry
 - Note: Due to small sample size, statistical inferences for this endpoint to be based on pooled data from Studies GX29176 and GX29185.
- Change from baseline in LLVA at Week 96 as assessed by ETDRS chart at a starting distance of 4 m
- Change from baseline in binocular maximum reading speed at Week 96 as assessed by MNRead or Radner Charts

A list of the hypothesis testing of the key secondary clinical endpoints is given below:

- H_{05} : There is no difference between lampalizumab and sham with regard to mean change from baseline in the number of absolute scotomatous points at Week 96.
- H_{06} : There is no difference between lampalizumab and sham with regard to mean change from baseline in LLVA at Week 96.
- H_{07} : There is no difference between lampalizumab and sham with regard to mean change from baseline in binocular maximum reading speed at Week 96.

For each lampalizumab dosing frequency and patient population found to be statistically different from sham for the test of the primary endpoint, testing of the three key secondary endpoints will be performed (e.g. if H_{01} is positive per the Type I error control plan, then the key secondary endpoints would be tested for the Q4W dose frequency in the overall patient population). The aim is to manage the Type I error rate with respect to conclusions about secondary endpoints within a given dose frequency and patient population. Thus, within each dose frequency and patient population, Type I error for key secondary endpoints will be controlled using a fixed sequencing approach by testing the secondary endpoint hypotheses sequentially in the order specified above, beginning with H_{05} .

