All hypotheses for the key secondary endpoints will be tested for significance at the study level, except for H₀₅. The secondary endpoint of number of absolute scotomatous points will be based on the microperimetry-analysis population, which is estimated to be 10-15% of the total ITT population. Microperimetry was assessed in a subset of patients at selected study sites only. For this secondary endpoint, data from both Studies GX29176 and GX29185 will be combined to achieve a sample size sufficient to evaluate and test for treatment differences with a reliable level of precision.

As a consequence of this, for analyses of secondary efficacy endpoints at the individual study level:

- For H₀₅, the study-level p-value will be presented. However, interpretation of significance in a confirmatory manner will be based on the analysis of pooled data from Studies GX29176 and GX29185.
- H₀₆ will be tested in a confirmatory manner at the study-level if and only if, based on an analysis of pooled data from Studies GX29176 and GX29185, H₀₅ is rejected (i.e., pooled analysis $p \leq 0.0496$).
- H₀₇ will be tested in a confirmatory manner at the study-level if and only if H₀₆ is rejected at the study-level

As noted above, significance testing for H₀₅ will not be done at the study level, but rather interpretation of significance in a confirmatory manner will be based on the analysis of pooled data from Studies GX29176 and GX29185 for the microperimetry-based endpoint.

All hypothesis tests for the secondary endpoints will be on the basis of a two-sided alpha level of 0.0496.

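### The SAP attaches formal Week 96 testing at an adjusted 0.0496 to the exploratory endpoints, and arguably to nine non-key secondaries, but the adjustment covers only iDMC reviews and only H05–H07 are ordered

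*SAP*

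**What the plan says.** Several parts of the SAP bear on which Week 96 results count as formal.

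- Section 2.1.2 opens its list of 12 endpoints with "The following secondary efficacy endpoints will be assessed over time up to Week 96, with formal statistical testing at Week 96". It then adds "Hypothesis testing for three key secondary endpoints will be performed in the order specified in Section 4.5.2.1 based on the Week 96 timepoint".
- Section 2.1.3 opens its list of 14 endpoints with "The following exploratory efficacy endpoints will be assessed over time up to Week 96, with formal statistical testing at Week 96".
- Sections 1 and 2.4 and the note under Table 3 describe the Week 48 look at secondary and exploratory endpoints as exploratory, "although formal statistical testing for these endpoints will be at Week 96".
- None of these sentences gives an alpha. The alpha is in the body of Table 3, in a column whose heading calls it adjusted: "0.0496 for secondary and exploratory endpoints tested at Week 96". For secondary endpoints, the last sentence of Section 4.5.2.1 repeats 0.0496 for all hypothesis tests.
- Section 3.2.2 explains the figure: "a nominal Type I error penalty of 0.0001 will be taken for each time the iDMC reviews unmasked data reports". It counts four reviews and applies 0.0496 to the primary endpoint. Section 2.3.2 gives the same explanation.
- Section 4.5.2.1 says "Significance testing for secondary efficacy endpoints will be gated on the success of the primary efficacy endpoint evaluated at Week 48". It lists three endpoints to be tested in order (H05, H06, H07), within each dose frequency and population. It uses confirmatory language only for these; for H05, "interpretation of significance in a confirmatory manner will be based on the analysis of pooled data from Studies GX29176 and GX29185".
- Section 4.5.3 plans the exploratory endpoints for the overall population and each biomarker subgroup, and allows the focus to depend on the primary results. It states no gate, order or correction.

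**The concern.** The SAP contrasts an exploratory look at Week 48 with formal testing at Week 96, so formal is meant to carry more weight than exploratory. It then gives that status, and an alpha described as adjusted, to a list of endpoints that it names exploratory. The section on Type I error management does not mention them.

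The case that matters is a drug that slows atrophy without helping vision. The primary endpoint succeeds, the gate opens, and every functional null is true. Read literally, the plan then allows a chance p<0.0496 on an unordered functional endpoint to be reported as a formal result at an adjusted level, although nothing has been adjusted for how many endpoints were tested. For the exploratory endpoints, the literal text does not even require the gate to be open.

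**Working it through.** **Where 0.0496 comes from.** The SAP does not print the starting alpha. Protocol Section 3.1.2 takes 0.0001 per review, expects five reviews and arrives at 0.0495, so the start is 0.0495 + 5 × 0.0001 = 0.05. With the SAP's four reviews, 0.05 − 4 × 0.0001 = 0.0496, which matches Table 3 exactly. The iDMC penalty uses the whole 0.0004, so none of the reduction is a correction for the number of endpoints.

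**Which endpoints have a rule.**

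| Set | Count | Gate | Order or correction |
|---|---|---|---|
| Key secondaries H05–H07 | 3 | Primary, same dose and population | Fixed sequence |
| Other secondaries in 2.1.2 | 12 − 3 = 9 | Primary, if tested at all | None |
| Exploratory endpoints in 2.1.3 | 14 | None stated | None |

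This leaves 9 + 14 = 23 endpoints outside any sequence.

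**What testing them as Table 3 says would do.** Take one dose and one population with every functional null true. Of the 14 exploratory endpoints, set aside the two based on GA area and the composite that includes GA area, since these need not be null if the drug slows atrophy. That leaves 11. Treat each test statistic as standard normal; two-sided 0.0496 gives a critical |z| of 1.963.

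If the k tests are independent, P(at least one p<0.0496) = 1 − 0.9504^k:

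- k = 9: 1 − 0.633 = 0.367
- k = 11: 1 − 0.571 = 0.429

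For two-sided tests on jointly normal statistics, independence gives the upper bound (Šidák's inequality). With equal correlation ρ, the probability is 1 − ∫ φ(c) [Φ((1.963 − √ρ c)/√(1−ρ)) − Φ((−1.963 − √ρ c)/√(1−ρ))]^k dc. Numerical integration gives:

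| Set | ρ = 0 (bound) | ρ = 0.5 | ρ = 0.7 | ρ = 0.8 |
|---|---|---|---|---|
| 9 non-key secondaries | 0.367 | 0.267 | 0.201 | 0.164 |
| 11 functional exploratory | 0.429 | 0.302 | 0.221 | 0.178 |
| 8 secondaries without microperimetry | 0.334 | 0.249 | 0.190 | 0.156 |
| 10 exploratory without microperimetry | 0.399 | 0.285 | 0.212 | 0.172 |

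The last two rows leave out the one microperimetry endpoint in each set, because inference on it uses data pooled with Study GX29185.

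The expected number of false rejections does not depend on the correlation. It is 9 × 0.0496 = 0.45 for the secondaries and 11 × 0.0496 = 0.55 for the functional exploratory endpoints. For the latter with both doses in one population, it is 22 × 0.0496 = 1.09.

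**The case against.** The strongest reply is that most of these passages concern timing. Table 3 is a timing table, and the sentences in Sections 1 and 2.4 say when analyses happen, not which claims may be made. Section 4.5.2.1 governs claims. It lists three endpoints to be tested, and its closing sentence on alpha follows directly and may mean only those. Section 2.1.2 points to it. Protocol Section 6.4.2 also gates and orders only three key secondaries, although the SAP states that it supersedes the protocol's analysis plan.

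Much of this stands for the 9 other secondaries. A reader might infer that the SAP definitely tests them at 0.0496 with only the gate as protection. The documents do not settle that. The opening of Section 2.1.2 and the gating sentence of 4.5.2.1 favour that reading; the three-item list favours the narrower one. On the narrower reading, the nine-endpoint figures do not apply.

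The reply does not dispose of the exploratory endpoints. The opening of Section 2.1.3 and the Table 3 row give them formal testing and an alpha, and no passage narrows this.

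It is also fair that the SAP explains the adjustment elsewhere (Sections 2.3.2 and 3.2.2), so a careful reader need not mistake it for an endpoint correction. The gate is a real protection too: if the primary fails for a dose and population, its secondaries are not tested.

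**Conclusion.** The inconsistency is real and firm for the 14 exploratory endpoints. For the 9 non-key secondaries it is an ambiguity that needs resolving. Followed as written, Table 3 lets an uncorrected p<0.0496 on an unordered endpoint count as a formal result.

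For illustration, with the gate open, no functional effect, and one dose and population, the chance of at least one such result is about 16% to 27% for the 9 secondaries and 18% to 30% for the 11 functional exploratory endpoints. This rests on assumed equal correlations of 0.8 to 0.5; the documents report none.

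Three stronger readings are not supported.

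- A reader might take 37% and 43% as the expected rates. They are upper bounds under independence, which is implausible here: the lists include BCVA change alongside a BCVA-loss responder, the NEI VFQ-25 composite alongside two of its subscales, and several versions of the same reading speed.
- A reader might infer that Sections 1, 2.1.2 and 2.1.3 and the text of 2.4 themselves assign 0.0496. They state no alpha.
- A reader might infer that H05–H07 are poorly controlled because error is managed separately within each dose and population. The SAP declares that as its aim, and it is not in question here.

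No conclusion on H01–H07 is affected.

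**What to change.** In SAP Sections 1, 2.1.2, 2.1.3 and 2.4, in Table 3 and its note, and in the last sentence of Section 4.5.2.1, limit formal testing at 0.0496 at Week 96 to H05–H07. State that p-values for the other 9 secondary endpoints and all 14 exploratory endpoints are nominal and descriptive. A footnote to Table 3 saying that the adjustment is the iDMC penalty (0.05 − 4 × 0.0001) would be a useful but optional clarification.

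The change is best made before the sponsor is unmasked for the Week 48 analysis, when the same endpoints are first examined, so that the choice between readings cannot depend on data.

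The cost is SAP wording only. The gate, order, alpha and power for H01–H07 and the sample size stay as they are. The sponsor gives up describing any of the other 23 results as formally significant.
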